Once the leg motor cortex of the more-affected side (left or right) has been identified via TMS, a tDCS device (Neuroelectrics Inc., Simi Valley, CA, USA) will deliver a small direct current through two sponge surface electrodes (3cm × 3cm, soaked with 15 mM NaCl)(Dundas et al. 2007). The anodal electrode will be placed over the representation of the motor cortex for the more affected leg, and a second electrode will be placed on the forehead above the contralateral orbit. The intensity of the tDCS will be 2 mA applied for 10 minutes, starting at 0 and increasing to 2 mA over a 30 second period of time. At the 9:30 time point the current will gradually be reduced from 2 mA to 0 mA. Anodal tDCS with these parameters has been reported to change the excitability of the leg motor cortex without inducing side effects (Jeffery et al. 2007). The used parameters are in accordance with a safety criterion and far below the threshold for tissue damage (Nitsche et al. 2003). The voltage during tDCS application will be less than 10 V. During the application of the tDCS current participants will perform strength testing for more-affected side using the same procedures as the initial MVC acquisition. All MVC will be collected within the 10 min tDCS stimulation time. Participants receiving a sham condition will only receive the initial 30 seconds of stimulation, after which the current will be set to 0. These parameters for sham stimulation were chosen based on previous reports that the perceived sensations on the skin, such as tingling, usually fade out in the first 30 s of tDCS (Nitsche et al. 2003; Paulus, 2003). The participants and the investigator performing the MVC testing will be blinded to the tDCS condition. Participants will not be told their strength values until the end of all testing sessions.

After completion of the tDCS/Sham strength assessment participants will perform a 6 minute walk test. The test will be performed in a cordoned off hallway with 2 cones placed 30 meters apart. Once the participants begin walking, a timer will be started and the distance covered every min will be recorded. Participants are allowed to stop and rest during the test if required. Every minute during the walk test participants will be asked their rating of perceived exertion (RPE, 0-10 scale) (Dalgas et al. 2014)

Strength Group Session 2

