After no less than 7 days, participants will return to the INPL to perform their final session. All procedures for Session 2 will be the same as in Session 1, except that participants who received tDCS will now receive sham stimulation and those that received the sham treatment will receive tDCS.

In all sessions both, participants and raters will be blinded to the intervention type. The experimenter who

will apply the intervention (real tDCS or Sham) will be different from the experimenter determining the outcome measures.

Fatigue Group Session 1

Once consent, questionnaires, and DXA have been completed, MVCs of the right and left knee extensors will be performed using the same methods stated before. After MVC performance participants will be asked which is their more-affected leg and this answer will be compared to the results of the MVC testing. Once the more-affected leg is determined the investigators will use the same TMS procedures as above to identify the more-affected leg's representation in the motor cortex. The anode tDCS electrode will then be placed in this spot, and stimulation will begin 5 min prior to the start of the fatigue task. After 30 secs the current will be lowered to 0 for the Sham group. The treatment group will receive stimulation until the end of the fatigue task or for an additional 15 min, whichever condition occurs first. tDCS blinding and procedures are the same as they are for the strength group. Both participant and investigator will be blinded to the treatment.

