tDCS is a non-invasive brain stimulation technique in which a very weak electrical current is applied to the scalp. tDCS has been conducted on humans and animals for many years and no evidence has emerged to suggest that it is harmful or has ever induced a serious side effect. However, the safety of tDCS is dependent on current strength, electrode size, and stimulation duration. Accordingly, these parameters have been investigated to establish safe and effective stimulation parameters for tDCS applications in research involving human subjects. The only side effects that have been reported when proper guidelines are followed are temporary tingling, itching, headache, or skin redness under the electrodes in some subjects. For example, a 2008 review of the approximately 100 human tDCS studies up until that time on healthy adults and patients found that 64 of these studies reported no side effects, 24 studies reported a temporary itching or tingling under the electrodes in some subjects, and one study reported skin redness. Furthermore, these slight side effects were of equal occurrence in subjects that received placebo stimulation in 7 studies. In addition, only two subjects in these 100 studies reported a mild headache. Similar findings have recently been reported in research and review articles (Nitsche et al. 2008; Hummel et al. 2008).

Physiological studies have also assessed the safety of tDCS when applied within the aforementioned stimulation guidelines. For example, there was no neuronal damage as measured by serum neuron-specific enolase (Stagg & Nitsche, 2011) or MRI measures of edema using contrast enhanced and diffusion-weighted MRI measures following administration of tDCS (Nitsche et al. 2004). Furthermore, tDCS did not negatively alter measures of neuropsychological function and EEG activity (Iver et al. 2005). Accordingly, rat studies using tDCS models emulating tDCS applied to humans (Liebetanz et al. 2009) showed that the current density needed to induce tissue damage or lesions was about 1429 mA/cm², whereas the current densities used in human studies are between 0.04 and 0.08 mA/cm² and in this proposal are 0.029 mA/cm². In conclusion, the tDCS stimulation parameters in this study are identical to the most common in the literature and have been proven to be exceptionally safe and well-tolerated.

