The probability is very unlikely that harm may occur (see above). Based on the available literature a slight headache should be the worst possible negative effect and should be very rare. In this case, non-prescription medication should relieve the headache within 1-2 hours.

Risks will be minimized by using safe, well-established procedures and strict monitoring of each experimental session. Risks are minimized by using stimulation parameters that are well-described, within international guidelines, and within the range of those used in hundreds if not thousands of studies (see above).

TMS safety

TMS is a non-invasive brain stimulation technique that can be used for both diagnostic and therapeutic procedures. The single and paired-pulse TMS techniques performed in this study have been used extensively in thousands of research studies and on tens of thousands of subjects in the United States and around the world. Single and paired pulse TMS techniques are considered very safe (Hallet, 2000, 2007) when accepted guidelines are followed (Wassermann et al. 1998). Finally, no long-term risks have been reported in the aforementioned review articles involving the use of TMS. In general, the risks associated with TMS are very minimal (Anand et al. 2002; Anderson et al. 2006; Loo et al. 2008). There is a very small risk of seizures if rTMS is done with very intense, high frequency stimulation or with trains of stimulation separated by a second or less (Anand et al. 2002; Anderson et al. 2006; Loo et al. 2008). Such intensity, frequency and repetition rate will not be used in this study as the study does NOT include rTMS and only single and paired pulse TMS methods will be employed. For most people, the single and paired pulse stimulation is not painful, but

occasionally slight discomfort or headache can occur. The headaches go away quickly with nonprescription medication. The noise caused by TMS pulses may affect hearing; therefore, subjects will be fitted with earplugs during TMS testing. Finally, there is no medical risk associated with the surface EMG recordings of the muscle responses to TMS.

2. **Psychological well-being.**

None

3. **Economic well-being.**

None

4. **Social well-being.**

None

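### The stated tDCS current density of 0.029 mA/cm² does not follow from 2 mA through 3 cm × 3 cm electrodes, which gives 0.222 mA/cm²: above, not below, the human range the protocol cites

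*Combined protocol and SAP*

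**What the plan says.** Section 2(a), Strength Group Session 1, specifies "two sponge surface electrodes (3cm × 3cm, soaked with 15 mM NaCl", and then "The intensity of the tDCS will be 2 mA applied for 10 minutes". One electrode is the active one: "The anodal electrode will be placed over the representation of the motor cortex for the more affected leg". The other goes on the forehead. For the fatigue group, section 2(a) states that "tDCS blinding and procedures are the same as they are for the strength group". No other current or electrode size appears anywhere in the protocol.

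Section 9(c)1, tDCS safety, names what safety depends on: "the safety of tDCS is dependent on current strength, electrode size, and stimulation duration". After giving a tissue-damage figure from rat studies, printed as 1429 mA/cm², it says that "current densities used in human studies are between 0.04 and 0.08 mA/cm² and in this proposal are 0.029 mA/cm²". It concludes that "the tDCS stimulation parameters in this study are identical to the most common in the literature" and that they are very safe. The next paragraph of the same section leans on this text: "The probability is very unlikely that harm may occur (see above").

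**The concern.** Current density is the current divided by the electrode's contact area, so the procedures section fixes it. The value printed in the risk section is far too small for the current and area given there.

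The direction matters as much as the size. With 0.029 mA/cm², a reader of section 9 sees a study working below the densities used in people. With the protocol's own settings, the study works above them. The protocol names current strength and electrode size as determinants of safety, and density combines the two. This sentence is also the only place where the study's dose is compared numerically with human use. An ethics reviewer relying on it would be given the comparison the wrong way round.

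If the slip is in the procedures section instead, the intervention itself is misdescribed, and staff following the text would deliver a dose that was not intended.

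**Working it through.** **Inputs**
- Current: 2 mA (section 2(a), Strength Group Session 1).
- Electrode: 3 cm × 3 cm, so 3 × 3 = 9 cm² each (same place).
- The fatigue group has the same tDCS procedures (section 2(a), Fatigue Group Session 1).
- Stated density 0.029 mA/cm²; stated human range 0.04 to 0.08 mA/cm²; damage figure as printed 1429 mA/cm² (section 9(c)1).

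**Formula:** density = current / contact area. The full current passes through each electrode, so the area of one electrode applies.

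**Attempt to reproduce 0.029**

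| Reading | Calculation | Density (mA/cm²) |
|---|---|---|
| One square electrode | 2 / 9 | 0.222 |
| Both electrodes pooled | 2 / 18 | 0.111 |
| Round electrode, 3 cm diameter | 2 / 7.07 | 0.283 |

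None gives 0.029. The pooled reading is the most generous, and it is still 0.111 / 0.029 = 3.8 times the stated value and 0.111 / 0.08 = 1.4 times the top of the range.

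**Could it be rounding?** Values that round to 0.029 run from 0.0285 to 0.0295.
- At 2 mA they need 2 / 0.0295 = 67.8 to 2 / 0.0285 = 70.2 cm².
- At 9 cm² they need 0.0285 × 9 = 0.257 to 0.0295 × 9 = 0.266 mA.

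Neither such an area nor such a current is in the protocol. Settings such as 1 mA over 35 cm² or 2 mA over 70 cm² would give 0.0286, so the figure may have been carried over from other settings. That is an assumption.

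**Size of the discrepancy, taking section 2(a) as correct**
- Against the stated figure: 0.2222 / 0.029 = 7.66.
- Against the top of the human range: 0.2222 / 0.08 = 2.78.
- Against the bottom of the human range: 0.2222 / 0.04 = 5.56.
- Margin to the printed damage figure: 1429 / 0.029 ≈ 49,300 as stated, and 1429 / 0.2222 ≈ 6,430 as recomputed.

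**What would put the study inside 0.04 to 0.08**
- At 2 mA: an electrode of 2 / 0.08 = 25 to 2 / 0.04 = 50 cm².
- At 9 cm²: a current of 0.04 × 9 = 0.36 to 0.08 × 9 = 0.72 mA.

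These are hypothetical. In either case 0.029 would still be wrong, because it lies outside the range: 1 − 0.029 / 0.04 = 27.5% below its lower end.

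**The case against.** The best reply is that this is a descriptive figure in a risk narrative and nothing operational uses it. The dosing instruction is 2 mA through 3 cm × 3 cm sponges. Endpoints, randomisation, sample size and the sham comparison do not involve the density. The 0.04 to 0.08 range is reported as usage, not as a limit. The recomputed density is still thousands of times below the printed damage figure. The protocol also offers support that does not depend on 0.029: a citation in section 2(a) for these parameters at the leg motor cortex, a review of about 100 human studies, and imaging, enzyme and neuropsychological evidence. The continuing review reports no adverse events, though only five participants had been studied.

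Most of this stands as a limit on the conclusion. It means that harm is not shown and that the minimal-risk rating is not shown to be wrong. The 6,430-fold margin is only as good as the printed 1429, which cannot be checked from the documents. None of it makes 0.029 correct or restores the direction of the comparison.

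A second reply is that the claim of parity with the commonest parameters concerns current, size and duration, not density, and that the protocol does not list the commonest values. That is fair: the conflict there is an inference from the protocol's own range. It is a reasonable one, since neither 0.029 nor 0.222 lies within 0.04 to 0.08, but it is secondary to the arithmetic.

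A third reply is that the electrode size or current may be the wrong entry, so that participants may have received a density inside the range. The documents leave that open. The protocol would still need correction, in the description of the intervention as well as the density.

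**Conclusion.** The concern holds. On the protocol's stated settings the density is 0.222 mA/cm², not 0.029: 7.7 times higher, and 2.8 times the top of the cited human range instead of below its bottom. No reading of 2 mA and 3 cm × 3 cm recovers the printed value, and the fatigue group's settings do not explain it.

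The 7.7-fold figure rests on section 2(a) being right about both current and electrode size. If it is not, the size of the error in the density changes and the methods text is also wrong. Either way, the two sections cannot both stand. The point corrects a stated safety comparison. It does not establish that participants were over-dosed or harmed.

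**What to change.** 1. Confirm from study records the electrode area and current actually delivered in both groups.
2. Restate the density in section 9(c)1 as current over area: 0.222 mA/cm² if section 2(a) is right. If it is wrong, correct section 2(a) and recompute.
3. Rewrite the comparison with 0.04 to 0.08 mA/cm², and qualify or remove the sentence saying the parameters match the commonest ones.
4. Re-read the statements that follow in section 9(c)1 and point back to this text, and the overall risk rating in section 9(a), against the corrected figure. Change the consent forms only if they repeat the density claim.

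While checking the settings, reconcile the stimulator: section 2(a) names a Neuroelectrics device and section 6 lists the ActivaDose II. This is a separate matter and does not affect the calculation.

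The cost is a wording amendment. If section 2(a) stands, the stated safety margin becomes less favourable. The Event History shows a final form submitted in July 2018, so the correction may now belong in the study record and in any report of the dose.

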*** Benefits, Procedures to Maintain Confidentiality ***

10. Benefits (Input N/A if not applicable)

a) Describe the potential benefit(s) to be gained by the subjects. If there is no direct benefit to the subjects describe how the results of the study may benefit society or a particular group.

There is no personal benefit associated with this protocol, although the outcomes may help improve rehabilitative procedures for people with MS who have fatigue and leg strength asymmetries.

11. Procedures to Maintain Confidentiality

a) Describe the procedures that protect the privacy of the subjects and maintain the confidentiality of the data. If a linked list is used, explain when the linked list will be destroyed. Provide a sample of the code that will be used, if applicable.

All data collected, including personal identifiable information will be stored either electronically on Colorado State University secured networks with access restricted to the current investigators. Hard copy data will be stored in a locked file cabinet that only research personnel have access too. At night second story of the Health and Exercise Science Department is restricted to authorized key holders, and the room in which the file cabinet is located is restricted to only current laboratory staff.

b) If information derived from the study will be provided to the subject's personal physician, a government agency, or any other person or group (other than the research team), describe to whom the information will be given and the nature of the information, if applicable.

N/A

c) Specify where and under what conditions study data will be kept, how samples will be labeled, who has access to the data, and what will be available and to whom. Federal regulations require that study data and consent documents be kept for a minimum of three (3) years after the completion of the study by the PI. For longitudinal projects and federally regulated studies, the PI may be required to keep the data and documents for a longer time period.

All data collected, including personal identifiable information will be stored either electronically on Colorado State University secured networks with access restricted to the current investigators. Hard copy data will be stored in a locked file cabinet that only research personnel have access too. At night second story of the Health and Exercise Science Department is restricted to authorized key holders, and the room in which the file cabinet is located is restricted to only current laboratory staff

* * * Potential Conflict of Interest * * *

12. Potential Conflict of Interest

Although you have already submitted CSU's official Conflict of Interest form (FCOI/COI/COC) to the University, it is the IRB's responsibility to ensure that conflicting interests related to submitted protocols do not adversely affect the protection of participants or the credibility of the human research protection program at CSU. Please answer questions a-d below. Please note that if you indicate that you have a potential financial or professional conflict of interest in relation to this protocol, your CSU FCOI/COI/COC Reporting Form must reflect this potential conflict. Link to CSU's Conflict of Interest policy: <http://www.facultycouncil.colostate.edu/files/manual/sectiond.htm#D.7.7>

a) N In connection with this protocol, do you or any of the protocol investigators or their immediate family members (i.e., spouse and legal dependents, as determined by the IRS) have a potential financial or professional conflict of interest?

b) N/A If you do have a potential conflict of interest, is this reported in your current FCOI/COI/COC?

c) N/A If you do have a potential conflict of interest, is there a management plan in place to manage this potential conflict?

d) N/A If you do have a potential conflict of interest, is this potential conflict of interest included in your consent document (as required in the Management Plan)?

If you have reported a possible conflict of interest, the IRB will forward the title of this protocol to your Research Associate Dean to complete your COI file.

For more information on CSU's policy on Conflict of Interest, please see the Colorado State University Academic Faculty and Administrative Professional Manual Sections D.7.6 & D.7.7.
<http://www.facultycouncil.colostate.edu/files/manual/sectiond.htm#D.7.7>

Link to CSU's Conflict of Interest Policy: http://www.provost.colostate.edu/index.asp?url=faculty_affairs.

*** * * Informed Consent * * ***

13. Informed Consent

NOTE: In order to complete this protocol, you must upload either a Consent Form or an Alteration of Consent Form (i.e., Cover Letter or Verbal Script) OR (if neither of those apply to your project) you must complete the Waiver of Consent information.

In the space below, please provide consent process background information for each Consent Form(s), Alteration of Consent Form(s), or Waiver(s).

Informed Consent

Title	Fatigue Consent 24July2017	
Consent Information Type	Consent	
Sponsor's Consent Version Number: (if any)		
Consent Form Template	 Attachment	Amendment_Consent_tDCS_Fatigue_24July2017 (1) (1)

[Consent Form Samples](http://ricro.colostate.edu/IRB/ConsentAssentTemplates.html)

Who is obtaining consent? The person obtaining consent must be knowledgeable about the study and authorized by the PI to consent human subjects.

How is consent being obtained?

What steps are you taking to determine that potential subjects are competent to participate in the decision-making process?

Title	Strength Consent 06JUNE2017	
Consent Information Type	Consent	
Sponsor's Consent Version Number: (if any)		
Consent Form Template	 Attachment	Consent_tDCS_Strength_201706 06 (4)

[Consent Form Samples](http://ricro.colostate.edu/IRB/ConsentAssentTemplates.html)

Who is obtaining consent? The person obtaining consent must be knowledgeable about the study and authorized by the PI to consent human subjects.

How is consent being obtained?

What steps are you taking to determine that potential subjects are competent to participate in the decision-making process?

***** Assent Background *****

14. Assent Background (Complete if applicable)

All minors must provide an affirmative consent to participate by signing a simplified assent form, unless the Investigator(s) provides evidence to the IRB that the minor subjects are not capable of assenting because of age, maturity, psychological state, or other factors.

See sample consent/assent forms at <http://ricro.colostate.edu/IRB/ConsentAssentTemplates.html>

Provide assent process background information, in the space below, for each Assent Form, Alteration Form (i.e., Cover Letter or Verbal Script), and Waiver.

Assent Background

15. HIPAA

Are you using PHI*? (See definition below)

Y

Colorado State University is a hybrid entity and does not have a research-related HIPAA policy. If you will be working with a HIPAA covered entity (e.g., Poudre Valley Health System), you will need to follow their HIPAA guidelines. If your project will involve a HIPAA-regulated entity, in the Attachment section (#16) please attach that entity's required HIPAA consent and/or each waiver of authorization or alteration of authorization requested (e.g., waiver of authorization for access to medical records). Include HIPAA authorization language in the consent document(s) as appropriate (e.g., when enrolling subjects).

*Protected Health Information (PHI) is health information with one or more of the following identifiers. For more information see: <http://www.hhs.gov/ocr/hipaa/>

1. Names
2. Social Security numbers
3. Telephone numbers
4. All geographic subdivisions smaller than a State, including street address, city, county, precinct, zip code, and their equivalent geocodes, except for the initial three digits of a zip code, if, according to the current publicly available data from the Bureau of the Census: (1) The geographic unit formed by combining all zip codes with the same three initial digits contains more than 20,000 people; and (2) The initial three digits of a zip code for all such geographic units containing 20,000 or fewer people is changed to 000
5. All elements of dates (except year) for dates directly related to an individual, including birth date, admission date, discharge date, date of death; and all ages over 89 and all elements of dates (including year) indicative of such age, except that such ages and elements may be aggregated into a single category of age 90 or older
6. Fax numbers
7. Electronic mail addresses
8. Medical record numbers
9. Health plan beneficiary numbers
10. Account numbers
11. Certificate/license numbers
12. Vehicle identifiers and serial numbers, including license plate numbers
13. Device identifiers and serial numbers
14. Web Universal Resource Locations (URLs)
15. Internet Protocol (IP) address numbers
16. Biometric identifiers, including finger and voice prints
17. Full face photographic images and any comparable images; and
18. Any other unique identifying number, character, or code (note this does not mean the unique code assigned by the Investigator(s) to code the research data)

16. Attachments

Attach relevant documents here. These could include: Collaborating Investigator's IRB approval and approved documents; Conflict of Interest information; Debriefing Script; Grant/Sub-contract; HIPAA Authorization Form from HIPAA-covered entity; Interview/Focus Group Questions; Investigator's Brochure; Letters of Agreement/Cooperation from organizations who will help with recruitment; Methodology section of associated Thesis or Dissertation project; Questionnaires; Radiation Control Office approval material; Recruitment Material (e.g., flyers, email text, verbal scripts); Sponsor's Protocol; Surveys; Other files associated with the protocol (you can upload most standard file formats: xls, pdf, jpg, tif, etc.) Please be sure to attach all documents associated with your protocol. Failure to attach the files associated with the

protocol may result in this protocol being returned to you for completion prior to being reviewed. Students: Be sure to attach the Methods section of your thesis or dissertation proposal. If this protocol is associated with a grant proposal, please remember to attach your grant.

To update or revise any attachments, please delete the existing attachment and upload the revised document to replace it.

Document Type	Questionnaire/Survey
Attachment	Beck_Depression_Inventory
Document Name	Beck_Depression_Inventory
Document Type	Questionnaire/Survey
Attachment	FSS
Document Name	FSS
Document Type	Other Protocol Material
Attachment	Timeline_tDCS
Document Name	Timeline_tDCS
Document Type	Other Protocol Material
Attachment	References
Document Name	References
Document Type	Other Protocol Material
Attachment	Device Accountability Log
Document Name	Device Accountability Log
Document Type	SOP
Attachment	RestingMotorThreshold_Hotspot_SOP
Document Name	RestingMotorThreshold_Hotspot_SOP
Document Type	Other Protocol Material
Attachment	Rossi2009_TMS_Safety
Document Name	Rossi2009_TMS_Safety
Document Type	Other Protocol Material
Attachment	HIPAA Release generic
Document Name	HIPAA Release generic
Document Type	Letters of Agreement.Cooperation
Attachment	[name] Letter _tDCS
Document Name	[name] Letter _tDCS
Document Type	Recruitment Material (e.g., flyers, email text, verbal scripts)

Attachment	Recruitment_Flyer_tDCS
Document Name	Recruitment_Flyer_tDCS
Document Type	Questionnaire/Survey
Attachment	MS_tDCS_pilot_screening_20170606
Document Name	MS_tDCS_pilot_screening_20170606
Document Type	SOP
Attachment	ActivaDoseII_manual
Document Name	ActivaDoseII_manual

